The best overall response is the best response recorded from the start of the treatment until disease progression/recurrence (taking as reference for progressive disease the smallest measurements recorded since the treatment started). The patient’s best response assignment will depend on the achievement of both measurement and confirmation criteria. Revised Response Evaluation Criteria in Solid Tumors (RECIST) Version 1.1 ([Eisenhauer 2009](#)) are summarized in the table:

**Response According to Revised Response Evaluation Criteria in Solid Tumors
(Version 1.1)**

Target Lesions	Non-Target Lesions	New Lesions	Overall Response	Best Overall Response when Confirmation is Required ^a
CR	CR	No	CR	≥4 weeks confirmation
CR	Non-CR/Non-PD	No	PR	≥4 weeks confirmation
CR	Not evaluated	No	PR	
PR	Non-CR/Non-PD/not evaluated	No	PR	
SD	Non-CR/Non-PD/not evaluated	No	SD	Documented at least once ≥4 weeks from baseline
PD	Any	Yes or No	PD	no prior SD, PR or CR
Any	PD*	Yes or No	PD	
Any	Any	Yes	PD	

CR=complete response; PD=progressive disease; PR=partial response; SD=stable disease.

^a In exceptional circumstances, unequivocal progression in non-target lesions may be accepted as PD.

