Regarding patients with unresectable locally advanced CSCC, tumor measurements for these patients will generally be performed with digital medical photography (bi-dimensional measurements). However, some patients may have deeply invasive target lesions in which tumor measurements can better be obtained with cross-sectional imaging (eg, MRI with gadolinium or CT with contrast). For any target lesions that are measured by cross-sectional imaging (MRI gadolinium or CT with contrast), measurements will be unidimensional according to RECIST 1.1.

Clinical Response Criteria for Externally Visible Tumors (for Groups 2, 4, 5, and 6 patients with locally advanced CSCC, and selected Groups 1, 3, 4, 5, and 6 patients in which target lesions are followed by digital medical photography)

A. Externally Visible Tumor Dimension

The externally visible component of target lesion(s) will be measured using bi-dimensional WHO criteria as the sum of the products (of individual target lesions) in the longest dimension and perpendicular second longest dimension at each tumor assessment and will be documented using

[REDACTED]

Clinical response criteria for externally visible tumor(s) require bi-dimensional measurements according to WHO criteria (reference), and are as follows:

- Complete response of externally visible disease (vCR): all target lesion(s) and non-target lesion(s) no longer visible, maintained for at least 4 weeks. Documentation of vCR requires confirmation by biopsies of site(s) of externally visible target lesion(s) with histologic confirmation of no residual malignancy, per central pathology review ([Appendix 5](#)). In the absence of such histologic confirmation, a patient cannot be deemed to have experienced vCR and the best response would be partial response.
- Partial response of externally visible disease (vPR): decrease of 50% (WHO criteria) or greater in the sum of the products of perpendicular longest dimensions of target lesion(s), maintained for at least 4 weeks
- Stable externally visible disease (vSD): not meeting criteria for vCR, vPR, or progressive disease
- Progression of visible disease (vPD): increase of $\geq 25\%$ (WHO criteria) in the sum of the products of perpendicular longest dimensions of target lesion(s). In rare cases, unequivocal progression of a non-target lesion may be accepted as vPD.

B. New Lesions

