4.5. Efficacy Variable

4.5.1. Primary Efficacy Variable

Overall response is based on **central-reviewed evaluation** at each time point at which a response assessment occurs using the RECIST version 1.1 (Appendix 1 of the protocol) or the composite response criteria (Appendix 2 of the protocol).

Best overall response (BOR) is determined once all the overall response data for the patient are known. The best overall response is the best response recorded during the study.

- Best overall response of CR or PR must be confirmed by consecutive evaluations of overall response of CR or PR at time points at least 4 weeks apart. In addition, locally advanced CSCC patients followed by digital medical photography require biopsy to confirm CR.
- Best overall response of SD must have met the response SD criteria at least once ≥ 39 days (6 weeks*7 days/week -3 days) after start of study treatment. Best overall

response of (early) PD does not require confirmation using the RECIST or the composite response criteria.

- The best overall response for patients who do not have any post-baseline tumor assessment will be not evaluable (NE). Patients with best overall response of NE will be considered as not reaching an objective response of CR or PR.

Objective response rate (ORR) is determined by the proportion of patients with best overall response of CR or PR in the FAS by group.

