4.5.2. Secondary Efficacy Variables

ORR based on investigator-assessed evaluation is also derived from the overall response that is based on investigator-assessed evaluation at each time point at which a response assessment occurs using the RECIST version 1.1 (Appendix 1 of the protocol) or the composite response criteria (Appendix 2 of the protocol).

Duration of response (DOR) is determined for patients with best overall response of CR or PR. Duration of response is measured from the time measurement criteria are first met for CR/PR (whichever is first recorded) until the first date of recurrent or progressive disease (radiographic or photographic), or death due to any cause. DOR by central-reviewed evaluation is the key secondary endpoint.

Patients who do not have a documented tumor progression or death will be censored at the last evaluable tumor assessment.

Progression-free survival (PFS) is measured from the start of treatment until the first date of recurrent or progressive disease (radiographic or photographic), or death due to any cause. Patients who do not have a documented tumor progression or death will be censored at the last evaluable tumor assessment. If a patient has no post-baseline tumor assessment, the patient will be censored at the first treatment date.

Overall survival (OS) is measured from the start of treatment until death due to any cause. Patients who do not have a survival event will be censored at the last date that patient is documented to be alive. As many patients may receive subsequent therapy after disease progression, a variant of OS will also be defined as censoring patients who do not have a survival event at the first date of a subsequent therapy is taken.

Time to tumor response (TTR) is determined for patients with BOR of CR or PR. TTR is measured from the start of treatment until the time measurement criteria are first met for CR/PR (whichever is first recorded).

For all of the above time-to-event variables, the time to event (day) is the date of event/censor the date of first study treatment+ 1.

CR rate is determined by the proportion of patients with best overall response of CR. Patients with best overall response of NE will be considered as not reaching an objective response of CR.

Disease control rate (DCR) is determined by the proportion of patients with BOR of CR, PR, or SD.

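### SAP 4.5.1 does not require a CR to be confirmed by a CR, so a CR seen once beside a PR can enter the CR rate, mainly in patients assessed by RECIST 1.1 only

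*SAP*

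**What the plan says.** SAP 4.5.1 takes the response at each visit from protocol Appendix 1 (RECIST 1.1) or Appendix 2 (composite criteria) and then sets its own rules for BOR. One sentence covers both grades of response: "Best overall response of CR or PR must be confirmed by consecutive evaluations of overall response of CR or PR at time points" at least four weeks apart. The same section states that "The best overall response is the best response recorded during the study". One further condition applies to CR alone: "locally advanced CSCC patients followed by digital medical photography require biopsy to confirm CR".

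SAP 4.5.2 then builds the secondary endpoint on BOR: "CR rate is determined by the proportion of patients with best overall response of CR". SAP 5.8.2 reports it by group with a 95% Clopper-Pearson interval. Estimating the CR rate by central review is a stated secondary objective for Groups 1 to 4 and Group 6 (protocol 2.2, SAP 1.2.2).

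Protocol Appendix 1 says that the patient's "best response assignment will depend on the achievement of both measurement and confirmation criteria". Its response table enters a confirmation of four weeks or more on the CR row. Appendix 2 defines complete response of externally visible disease as "all target lesion(s) and non-target lesion(s) no longer visible, maintained for at least 4 weeks", and adds histologic confirmation that no malignancy remains.

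**The concern.** The SAP pools CR and PR on both sides of its sentence: either grade is confirmed by a neighbouring evaluation of either grade. Together with a BOR that is the best response recorded, a PR next to a single CR is enough to make BOR equal to CR. Nothing else in the SAP says that a CR needs a second CR.

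Two programmers could follow the SAP faithfully and report different CR rates. If the literal rule is programmed, any error goes one way, upward.

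Timing adds to this. The primary cut-off is six months after the last patient starts treatment (SAP Section 5), and the Group 6 interim asks for 28 weeks, or three tumour assessments (SAP Section 8). A patient with a PR at the second scan and a first CR at the third would already count as a confirmed CR. At stake are the secondary CR rate, its interval, and the split of BOR between CR and PR.

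**Working it through.** The plan gives no expected CR rate, null value or power for CR, so there is no CR figure to reproduce. The check is a classification exercise, followed by the arithmetic per patient.

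**1. Two rules applied to the same scans.** Scans are 8 or 9 weeks apart, so any two consecutive scans meet the four-week interval. The literal rule needs a consecutive pair in which each member is CR or PR, and BOR is the better member. The CR-by-CR rule gives CR only for a CR, CR pair. Any other pair of PR or better gives PR.

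| Scan sequence | Literal SAP rule | CR-by-CR rule |
|---|---|---|
| PR, PR, CR | CR | PR |
| PR, CR, PD | CR | PR |
| PR, CR, PR | CR | PR |
| CR, PR, PR | CR | PR |
| PR, CR, CR | CR | CR |
| CR, CR | CR | CR |
| CR, PD | no confirmed response | no confirmed response |
| SD, CR, PD | no confirmed response | no confirmed response |

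The first four rows differ. In each of them the patient is a responder under both rules.

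**2. What this leaves unchanged.** ORR counts CR and PR alike, so it is identical under both rules. DOR starts at the first CR or PR, DCR counts CR, PR and SD together, and PFS does not use BOR. None of them moves.

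**3. Who is exposed.** For disease followed by photography, the Appendix 2 definition that the SAP adopts at each visit already contains the four-week maintenance and the negative biopsy. For disease followed by RECIST 1.1 only, the pooled sentence is the SAP's only confirmation rule for CR. Groups 1 and 3 are entirely metastatic. Group 6 may enrol up to 133 metastatic patients out of 167 (protocol 9.2). Protocol 6.3.2 expects most metastatic patients to be followed by RECIST 1.1 only.

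**4. Size per patient.** Each reclassified patient changes the CR rate by 1/N:
- Group 6, planned N=167: 1/167 = 0.6 points
- Group 1, enrolled N=59: 1/59 = 1.7 points
- Group 3, enrolled N=56: 1/56 = 1.8 points

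**5. Illustration only.** Neither input here is in the documents. Assume that the literal rule gives a CR rate of 10% to 20% in Group 6, and that 10% to 30% of those CRs rest on a PR.
- 17/167 = 10.2% would fall to between 15/167 = 9.0% and 12/167 = 7.2%.
- 33/167 = 19.8% would fall to between 30/167 = 18.0% and 23/167 = 13.8%.

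**The case against.** The strongest reply is that the sentence can be read respectively: CR confirmed by CR, PR by PR. The SAP takes visit-level response from the protocol appendices, and SAP 1.2.4 does not list CR confirmation among its departures from the protocol. SAP Section 5 also allows up to three more months so that a CR or PR arising at six months can be confirmed, which fits an intent that a new CR is itself confirmed. Response data continue to be collected after the primary analysis, so a last-scan CR can be resolved later. The CR rate is descriptive, with no test attached.

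Part of this stands. The wording is ambiguous, the consequence is confined to a descriptive secondary endpoint, and longer follow-up shrinks it. But the respective reading is strained: PR then CR would then not be confirmed even as a response, and PR, CR, PD would leave the patient a non-responder. The cut-off sentence does not settle the matter, because on the literal rule PR then CR needs no further confirmation. Nor can the Appendix 1 confirmation column be assumed to carry over. The SAP writes its own BOR rules, for example at least 39 days after the start of treatment for SD, where Appendix 1 has four weeks from baseline.

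A reader might go further and infer that the protocol requires every CR to be maintained for four weeks. It does not. That wording belongs to externally visible disease and ulcerated lesions in Appendix 2. Appendix 1 asks for confirmation without naming the confirming response, and it puts the same entry on a PR row.

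**Conclusion.** The point holds as a defect in the SAP's confirmation rule. Read literally, it admits to the CR rate a CR supported only by an adjacent PR. This fits poorly with the confirmation that Appendix 1 attaches to the CR row, and it matters mainly for patients assessed by RECIST 1.1 only. The main routes are PR then CR at the last scan, and PR, CR, PD. CR followed by PR should be uncommon: from a zero sum of diameters, regrowth of 5 mm or more already meets the Appendix 1 definition of PD.

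The supported size is 1/N per affected patient, as shown above. The total cannot be stated, because the documents give neither the number of CRs nor how many rest on a PR. The conclusion assumes that the rule is programmed as written.

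Two stronger inferences are not supported. A lone CR with no CR or PR beside it is not counted under the literal rule or the CR-by-CR rule. The primary endpoint is also not inflated, since every sequence on which those two rules differ is a responder under both.

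**What to change.** Replace the pooled sentence in SAP 4.5.1 with three statements:

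- A BOR of CR requires two consecutive overall responses of CR at least four weeks apart, plus a negative biopsy where required.
- A BOR of PR requires two consecutive overall responses of PR or better at least four weeks apart that do not meet the CR rule.
- A CR supported only by an adjacent PR counts as PR.

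Apply the same rule to central and investigator BOR. Do not add central adjudication of a CR followed by PR. If the later scan were recast as PD, the response could become unconfirmed, and ORR could then change.

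The cost is a short SAP revision before the final database lock and a small change to the BOR derivation. The reported CR rate may be slightly lower. ORR, DOR, PFS and DCR as derived under the literal rule stay the same.

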4.5.2. Secondary Efficacy Variables

ORR based on investigator-assessed evaluation is also derived from the overall response that is based on investigator-assessed evaluation at each time point at which a response assessment occurs using the RECIST version 1.1 (Appendix 1 of the protocol) or the composite response criteria (Appendix 2 of the protocol).

Duration of response (DOR) is determined for patients with best overall response of CR or PR. Duration of response is measured from the time measurement criteria are first met for CR/PR (whichever is first recorded) until the first date of recurrent or progressive disease (radiographic or photographic), or death due to any cause. DOR by central-reviewed evaluation is the key secondary endpoint.

Patients who do not have a documented tumor progression or death will be censored at the last evaluable tumor assessment.

Progression-free survival (PFS) is measured from the start of treatment until the first date of recurrent or progressive disease (radiographic or photographic), or death due to any cause. Patients who do not have a documented tumor progression or death will be censored at the last evaluable tumor assessment. If a patient has no post-baseline tumor assessment, the patient will be censored at the first treatment date.

Overall survival (OS) is measured from the start of treatment until death due to any cause. Patients who do not have a survival event will be censored at the last date that patient is documented to be alive. As many patients may receive subsequent therapy after disease progression, a variant of OS will also be defined as censoring patients who do not have a survival event at the first date of a subsequent therapy is taken.

Time to tumor response (TTR) is determined for patients with BOR of CR or PR. TTR is measured from the start of treatment until the time measurement criteria are first met for CR/PR (whichever is first recorded).

For all of the above time-to-event variables, the time to event (day) is the date of event/censor the date of first study treatment+ 1.

CR rate is determined by the proportion of patients with best overall response of CR. Patients with best overall response of NE will be considered as not reaching an objective response of CR.

Disease control rate (DCR) is determined by the proportion of patients with BOR of CR, PR, or SD.

Durable disease control rate (dDCR) is defined as the proportion of patients best overall response of CR, PR, or SD without progression for at least 16 weeks (allowing tumor assessment made 1 week earlier than week 16).

Patient-reported quality of life is measured by the EORTC QLQ-C30 (Appendix 1 of protocol) on day 1 of every cycle (Aronson, 1993). The global health status/QoL, five functional scales (physical, role, cognitive, emotional and social), and three symptom scales (fatigue, pain, nausea and vomiting) and a number of single items assessing additional symptom commonly reported by cancer patients (dyspnoea, loss of appetite, insomnia, constipation and diarrhoea) and perceived financial impact of the disease will be computed using the QLQ-C30 scoring procedures (Fayers, 2001). Change scores are defined as change of summary score of EORTC QLQ-C30 from day 1 of first treatment cycle.

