5.7.2. Prohibited Medications and Concomitant Treatments

While participating in this study, a patient may not receive any standard or investigational agent for treatment of a tumor other than cemiplimab as mono therapy. **After communication with the sponsor, focal palliative treatment (eg, radiation) would be allowed for local control of a tumor once a patient has completed 24 weeks of study treatment.** Any other medication which is considered necessary for the patient's welfare, and which is not expected to interfere with the evaluation of the study drug, may be given at the discretion of the investigator.

Patients using immunosuppressive doses (>10 mg per day of prednisone or equivalent) of systemic corticosteroids other than for corticosteroid replacement will not be eligible for the study. It is recommended that patients do not receive systemic corticosteroids such as hydrocortisone, prednisone, prednisolone (Solu-Medrol[®]) or dexamethasone (Decadron[®]) at any time throughout the study except in the case of a life-threatening emergency and/or to treat an irAE. Physiologic replacement doses of systemic corticosteroids are permitted, even if >10 mg/day prednisone equivalents. A brief course of corticosteroids for prophylaxis (eg, contrast dye allergy) or for treatment of non-autoimmune conditions (eg, delayed-type hypersensitivity reaction caused by contact allergen) is permitted.

Note: Bisphosphonates and denosumab are not prohibited.

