5.7.4. Radiation Therapy

Radiation therapy is not part of the study regimen. Patients for whom radiation therapy is planned are not eligible. If during the course of the study, a patient develops a symptomatic lesion for which palliative radiation therapy is deemed appropriate by the investigator, this will be deemed

PD and generally the patient would be removed from study. Palliative radiation therapy may be allowed in certain circumstances in patients who have been on study for at least 24 weeks (see Section 5.7.2). Such cases must be discussed with the medical monitor prior to any radiation therapy if the investigator feels that restarting cemiplimab after radiation is in the best interest of the patient. The patient will be deemed to have experienced disease progression if radiation therapy is instituted but will be followed for OS.

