APPENDIX 10. STATISTICAL ANALYSES

ESTIMANDS

For Group 6 primary analysis, the statistical methods for the primary and secondary endpoints will be consistent with that which was done for Groups 1 to 3. This will facilitate a meaningful comparison of Group 6 with the previous groups. Additional statistical analyses will also be performed, including sensitivity analyses for DOR and PFS assuming informative censoring for intercurrent event.

Attributes for ORR per Central Review and Investigator Assessment

1. The study population is defined as CSCC patients who are enrolled on the protocol.
2. The endpoint is ORR, defined as the proportion of patients with BOR of CR or PR. ORR per central review is the primary endpoint, and ORR per investigator assessment is a secondary endpoint.
3. Intercurrent events and how to account for these events are described in [Table 16](#).
4. Estimated ORR will be provided, along with the 2-sided 95% exact binomial confidence interval using the Clopper-Pearson method.

Table 16: Intercurrent Events for Analysis of ORR per Central Review and Investigator Assessment

Intercurrent events	Rules of imputing data in primary analysis
Initiation of palliative radiation therapy	Patient will be considered to have PD at time of initiation of radiation (Section 5.7.4 of protocol).
Surgical removal of target lesion	BOR will be considered as PR if no prior PD is observed (Section 5.7.3 of protocol).
Unconventional responses (eg, a patient first experience PD and then CR or PR)	BOR will be considered as PD.
No evaluable postbaseline tumor assessment	BOR will be deemed NE. Patient with BOR of NE will be included in the ORR analysis as a non-responder.

A sensitivity analysis will be performed for ORR where the intercurrent events of “initiation of palliative radiation therapy” and “surgical removal of target lesion” will be ignored. Patients with unconventional responses will be considered as responders. Patients with BOR of NE will be excluded from this analysis.

Attributes for DOR per Central Review and Investigator Assessment

1. The study population is defined as CSCC patients who are enrolled on the protocol and had a CR/PR response.
2. The endpoint is DOR, measured from the time measurement criteria are first met for CR/PR (whichever is first recorded) until the first date of recurrent or progressive disease or death due to any cause in patients with BOR of CR or PR.

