3. Intercurrent events and how to account for these events are described in [Table 17](#).
4. DOR will be summarized by median and its 95% confidence interval by the Kaplan-Meier method.

Table 17: Intercurrent Events for Analysis of DOR per Central Review and Investigator Assessment

Intercurrent events	Rules of imputing data in primary analysis	Sensitivity analysis
Initiation of radiation therapy	Patient will be considered to have PD at time of initiation of radiation.	
Surgical removal of target lesion	DOR will be censored at time of surgery if no prior PD or death is observed.	
No evaluable post-baseline tumor assessment (BOR=NE)	Patient will be deemed as a non-responder and will not be included in the DOR analysis.	
Lost to follow-up Or Discontinuation of study in patients with BOR of CR or PR	DOR will be censored at last valid tumor assessment if no PD or death is observed.	If a patient discontinued study due to PD or AE, this patient will be considered to have DOR event on the end of study date. *

A sensitivity analysis will be performed for DOR where the intercurrent events of “initiation of palliative radiation therapy” and “surgical removal of target lesion” will be ignored. Patients with unconventional responses will be included in this analysis where DOR is measured from time of first response to first PD after the response or death, whichever is earlier. The analysis will only include patients with BOR of CR or PR. DOR for patients who don’t have PD or death will be censored at last valid tumor assessment.

Attributes for PFS per Central Review and Investigator Assessment

1. The study population is defined as CSCC patients who are enrolled on the protocol.
2. The endpoint is PFS, measured from time of enrollment until the first date of recurrent or progressive disease, or death due to any cause.
3. Intercurrent events and how to account for these events are described in [Table 18](#).
4. PFS will be summarized by median and its 95% confidence interval by the Kaplan-Meier method.

Table 18: Intercurrent Events for Analysis of PFS per Central Review and Investigator Assessment

Intercurrent events	Rules of imputing data after intercurrent events for primary analysis	Sensitivity analysis
Initiation of radiation therapy	Patient will be considered to have PD at time of initiation of radiation.	
Unconventional responses (eg, a patient first experience PD and then CR or PR)	Patient will be considered to have PD at time of first PD.	

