4.4. Rescue Medication/Prohibited Medication

While participating in this study, a patient may not receive any standard or investigational agent for treatment of a tumor other than cemiplimab as monotherapy. Any other medication which is considered necessary for the patient's welfare, and which is not expected to interfere with the evaluation of the study drug, may be given at the discretion of the investigator.

Patients using immunosuppressive doses (>10 mg per day of prednisone or equivalent) of systemic corticosteroids other than for corticosteroid replacement will not be eligible for the study. It is recommended that patients do not receive systemic corticosteroids such as hydrocortisone, prednisone, prednisolone (Solu-Medrol®) or dexamethasone (Decadron®) at any time throughout the study except in the case of a life-threatening emergency and/or to treat an immune-related adverse event (irAE). Physiologic replacement doses of systemic corticosteroids are permitted, even if >10 mg/day prednisone equivalents. A brief course of corticosteroids for prophylaxis (eg, contrast dye allergy) or for treatment of non-autoimmune conditions (eg, delayed-type hypersensitivity reaction caused by contact allergen) is permitted.

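### The protocol makes the start of radiation a progression event in the primary DOR and PFS analyses; the SAP's event definition drops it and does not say so

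*SAP*

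**What the plan says.** **Protocol.** Section 5.7.4 states: "The patient will be deemed to have experienced disease progression if radiation therapy is instituted but will be followed for OS". The primary-analysis columns of Appendix 10 Table 17 (DOR) and Table 18 (PFS) carry the rule and date it: "Patient will be considered to have PD at time of initiation of radiation". For surgical removal of a target lesion, Table 17 states: "DOR will be censored at time of surgery if no prior PD or death is observed". Table 18 has no surgery row. The text after the tables makes ignoring radiation (DOR and PFS) and surgery (DOR) a sensitivity analysis. Appendix 10 opens by stating how the primary analysis of Group 6 is to be run: "the statistical methods for the primary and secondary endpoints will be consistent with that which was done for Groups 1 to 3". Radiation on study is foreseen in 5.7.2, provided the sponsor has been contacted: "focal palliative treatment (eg, radiation) would be allowed for local control of a tumor once a patient has completed 24 weeks of study treatment".

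**SAP.** Section 4.5.2 runs both DOR and PFS "until the first date of recurrent or progressive disease (radiographic or photographic), or death due to any cause". A patient with neither is censored at the last evaluable tumor assessment. The summary table in 11.1 shortens the qualifier to radiographic for both endpoints. The SAP has no rule for radiation or target-lesion surgery during the study and never cites Appendix 10. Section 1.2.4, which lists departures from the protocol, names only added endpoints (TTR, DCR, dDCR) and one extra ORR sensitivity analysis.

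**The concern.** Starting radiation is neither a radiographic nor a photographic finding. A programmer who follows SAP 4.5.2 exactly will not count it as an event. On radiation, the SAP's main DOR and PFS analyses then do what the protocol reserves for a sensitivity analysis, and nothing tells the reader so. The SAP calls DOR by central review its key secondary endpoint. The same patient could be an event under the protocol's estimand and censored, or still in response, under the SAP.

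Surgery on a target lesion raises a narrower version of the problem. The protocol stops DOR follow-up at that point, whereas the SAP goes on using whatever assessments follow.

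**Working it through.** There is no sample size, power or alpha figure to reproduce. The check compares the rules, works one example with assumed dates, and bounds the frequency.

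**1. Rules side by side**

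| Occurrence | Protocol primary analysis | SAP 4.5.2 |
|---|---|---|
| Radiation starts, DOR | Event on that date (Table 17) | Not an event |
| Radiation starts, PFS | Event on that date (Table 18) | Not an event |
| Target lesion removed, DOR | Censored at surgery (Table 17) | No rule; follow-up continues |
| Target lesion removed, PFS | No rule (Table 18) | No rule |

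The documents differ in the first three rows only.

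**2. One irradiated patient**

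Assumed dates, in weeks from first dose: scans every 9 weeks, first response at week 9, radiation at week 30, radiographic progression at week 54. (The protocol starts PFS at enrollment and the SAP at first dose. That separate difference is left aside.)

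- Protocol: DOR event at 30 − 9 = 21 weeks; PFS event at 30 weeks.
- SAP, patient leaves the study at radiation, last scan at week 27: DOR censored at 27 − 9 = 18 weeks; PFS censored at 27 weeks.
- SAP, assessments continue: DOR event at 54 − 9 = 45 weeks; PFS event at 54 weeks. Without later progression, the patient is censored at the last scan instead.

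**3. Direction for radiation**

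Suppose the patient leaves. Let n be the number at risk just after the last scan, this patient included. Let k be the number of other events between that scan and the radiation date, with no other censoring. Over that interval the Kaplan-Meier estimate is multiplied by:

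- protocol: (n − k − 1)/n
- SAP: (n − k − 1)/(n − 1)

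The SAP factor is larger, so the curve is higher from the radiation date onward. If assessments continue, the curve is higher from radiation until the later event. What happens after that depends on how many remain at risk. Overall the SAP rule favours longer DOR and PFS.

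**4. Direction for surgery**

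Replacing a censoring with continued follow-up may add event-free time or a later event. The effect on DOR has no fixed sign.

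**5. How often**

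Protocol Table 20, Groups 1 to 3:

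- patients: 59 + 78 + 56 = 193
- radiation: 0 + 0 + 0 = 0
- surgical removal of a target lesion: 1 + 0 + 0 = 1
- exact two-sided 95% upper limit for 0/193: 1 − 0.025^(1/193) = 0.0189, about 1.9%
- applied to Group 6: 167 × 0.0189 = 3.2, about 3 patients

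**The case against.** **The SAP inherits the protocol rule.** It is based on Amendment 9, which contains Appendix 10, and its list of departures does not mention radiation. The parenthesis could be read as naming assessment methods and leaving Appendix 10 in force. This is a fair reading of intent, but the text does not secure it. Section 4.5.2 gives a complete event and censoring rule. The SAP cites protocol Appendices 1, 2 and 9 but not 10. It also writes out comparable rules elsewhere: an OS variant censored at subsequent therapy, and censoring at the first SC dose.

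**The time does not simply run on.** A reader might infer that an irradiated patient always keeps accruing DOR and PFS under the SAP. The protocol does not support that. Section 5.7.4 says such a case is deemed "PD and generally the patient would be removed from study", with exceptions after 24 weeks, and Table 9 requires follow-up scans only if progression has not already been confirmed. The usual effect is an event turned into a censoring; the longer times arise only if assessments continue. This objection stands.

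**Surgery.** A reader might infer that the surgery gap lengthens both endpoints. It does not touch PFS, because Table 18 has no surgery rule, and its effect on DOR can go either way.

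**Frequency.** Table 20 shows almost no such cases, and Appendix 10 expects similar rates in Group 6. This largely stands. The counts come from the primary analysis, about 6 months after each group's last patient started. The Group 6 primary analysis has a similar horizon, so they are a reasonable guide to it. They are weaker for later updates, since Group 6 treatment runs to 108 weeks.

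**SAP 4.4.** This section says "a patient may not receive any standard or investigational agent for treatment of a tumor other than cemiplimab as monotherapy" and omits the protocol's 24-week radiation allowance. A reader might treat that as part of the defect, but the omission changes no estimate.

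**Conclusion.** The mismatch is real and undeclared. As written, the SAP drops an event that the protocol's primary DOR and PFS analyses require, and drops a DOR censoring rule for surgery. For radiation the direction favours longer DOR and PFS; for surgery only DOR is affected, with no fixed direction.

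The expected size is small: about 3 of 167 Group 6 patients at the upper limit for radiation, assuming the Group 6 rate resembles that in Groups 1 to 3 at their primary analysis. The week counts in the example rest on assumed dates and show only the mechanism.

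A reader might infer that the trial's efficacy conclusion is at risk. The documents do not support that: SAP 5.8.1 judges each group on ORR alone, and DOR and PFS are Kaplan-Meier summaries with no threshold. The reason to correct it is that the event rule for the key secondary endpoint should be the same in both documents.

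**What to change.** - In SAP 4.5.2 and 11.1, state that the primary DOR and PFS analyses follow protocol Appendix 10 Tables 17 and 18. The start of radiation is a progression event on that date for both endpoints, and DOR is censored at surgical removal of a target lesion if there was no earlier progression or death.
- Name the version that ignores these events as the sensitivity analysis, as Appendix 10 does.
- Carry the Table 16 rules into SAP 4.5.1, which lacks the radiation and surgery rules for best overall response. Otherwise the responders entering the DOR analysis may not match the protocol's.
- Align the progression wording in 11.1 with 4.5.2.

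No change to SAP 4.4 is needed for this point. The cost is a few sentences that copy rules the protocol already states. The downside is that DOR and PFS may look slightly less favourable if radiation occurs.
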